#### 2.4.1. Preoperative Procedures

The investigator will determine and document on CRFs whether each patient meets the selection criteria previously outlined before enrollment into the study. He will also obtain informed consent for study participation from each patient prior to enrollment. A copy of the informed consent form will be kept by the investigator in the patient's study notebook. Patients not meeting the selection criteria or not receiving informed consent **should not** be enrolled in the study.

The investigator will determine and record on CRF1 each patient's demographics and relevant medical history, i.e., New York Heart Association (NYHA) functional class, cardiac rhythm, preoperative conditions, and diagnosis for valve replacement, etc. A preoperative echo/Doppler evaluation of the valve(s) being replaced is required according to the procedures of this study; a cardiac catheterization is not requested.

Blood studies on each patient will include: white blood cell count, red blood cell count, hemoglobin, hematocrit, serum lactate dehydrogenase (with fractionation by isoenzymes if above normal), plasma free hemoglobin, reticulocyte count, and haptoglobin. This will be recorded preoperatively, if possible, and at both follow-up intervals. The laboratory report including normal ranges will suffice as a CRF for these tests.

Specific Instructions for Form CRF1

These instructions are made to assist the study coordinator in filling out the form. Complete all items on the form. If information is unavailable to answer any item, make a note on the form. When asked to specify a particular answer, use a short description. On all check off lists, the space to be checked is either in front of, or below the answer. Please check any and all items that apply to the patient.

For patient study ID use patient initials. NYHA functional class uses the generally familiar nomenclature of that association. For the purposes of this study the commonly used classes of IIa and IIb are not used, either subgroup is considered class II. For infants and toddlers the Ross Scale functional classification can be substituted for NYHA classification anytime this data element is requested.

Previous cardiovascular surgery, and for pediatric patients pediatric comorbidities, should be noted with a one or two word name of surgery and the date performed (page 2 of CRF1). Room is given for three prior procedures. Attach a separate explanation if more prior surgery was done. For coronary artery bypass surgery, please note the number of grafts by the following notation: CABG x 2 = double graft; CABG x 3 = triple graft; and so on.

If the patient has been maintained on any permanent, preoperative anticoagulant therapy, the most recent available preoperative INR should be measured and recorded.

#### 2.4.2 Operative Procedures

The surgical technique employed is that developed and perfected by the principal investigator in his normal practice of cardiac surgery. Operative details such as cardioplegia are not specified in the protocol.

An echo/Doppler assessment of the study valve(s) is required on each patient just prior to discharge (CRF2). The echocardiography tapes will also be provided to the sponsor, each echo exam on each patient will be recorded on a separate tape.

The investigator will record on CRF3 information regarding the particular valve(s) implanted and other details concerning the surgery such as suture technique and any concomitant procedures. The implantation data card contained in the valve package will be provided to the distributor within 24 hours of the surgery.

Specific Instructions for Form CRF3

Use the patient study ID assigned on the preoperative form (CRF1) to identify the patient. Check any and all of the items that apply to this patient. Where explanations are needed, print a brief description of the required data.

Carefully record the valve position, size and serial number. For concomitant procedures, there are spaces for these additional procedures. Write in the name of the procedure done. For coronary artery bypass grafting, also note the number of grafts (i.e., CABG  $\times$  2 = double graft, CABG  $\times$  3 = triple graft, and so on).

Where requested, attach additional CRFs or reports. Also any appropriate intraoperative hemodynamic evaluation form, or complication form is required.

#### 2.4.3 Early Postoperative/Discharge Procedures

The investigator will record the date of the patient's discharge from the hospital and the date of the early follow-up examination on CRF4. The discharge follow-up exam records the patient's status at the time of discharge or at 30 days, whichever comes

first. The patient's NYHA and cardiac rhythm status and any complications will be noted along with the patient's antithromboembolic therapy. It is important to record the international normalized ratio (INR) at the time of the exam. Wherever possible this value should be within the therapeutic range described below **before** a patient is discharged from the hospital.

Mechanical heart valve recipients should be maintained continuously on anticoagulant therapy, except where contraindicated. Postoperatively, the continuous warfarin (tradename Coumadin®) therapy shall maintain the following therapeutic levels of INR: 2.0 to 3.0 for aortic valves. These procedures generally follow guidelines published by various medical societies.

Preoperative echocardiograms on the dysfunctional valve being replaced, predischarge, 3-6 month and one year postoperative Doppler echocardiograms on the study valve are required for each patient. At each postoperative assessment, the investigator will need to determine the patient's availability for future follow-up. If any patient needs to be seen at other than a regularly scheduled follow-up visit, the same follow-up information as required at regular times will be documented by the investigator on the follow-up form, and that follow-up will be indicated as an interim visit.

#### 2.4.4 Late Follow-up Reporting

Late follow-up is required in the 3-6 month postoperative interval, and at 1-year (between 11 and 14 months postoperatively). Follow-up must be in person; telephone or questionnaire follow-up is unacceptable. A late follow-up form (CRF4) is due at each follow-up on each patient whether or not follow-up has occurred.

Late follow-up information includes in all cases the patient ID, cardiac rhythm (from electrocardiogram or echocardiogram), NYHA classification, and anticoagulant therapy information, including INR. Blood samples shall be drawn and forwarded to the local laboratory at each regularly scheduled late follow-up. These samples are the same as the preoperative tests and are handled in the same manner. Echocardiography studies are required at the 3-6 month and 1-year follow-up. Those data should be included at that time, but should also be added when done optionally at any other follow-up. For any new complication, a complication report (CRF5) must be completed and attached. All complications that have occurred between follow-up examinations must be reported on the appropriate form.

#### 2.4.5 Complication Reporting

All complications should be recorded by the investigator on the proper complication form, CRF5. Start and stop dates and etiology should be noted. The investigator will attempt to evaluate the relationship of all deaths, reoperations, explants, or cardiovascular complications to the study valve as presented in the AATS/STS guidelines and will provide pertinent details of the event on the CRF. Copies of autopsy report and/or death summary must be included where applicable. Every effort should be made to return any explanted valve(s) (at autopsy or reoperation) to the

sponsor, see section 2.4.8. Please complete CRF6. Return kits for explanted valves can be provided by the sponsor.

The investigator will report any serious or unexpected complication occurring during the investigation to the monitor within 24 hours, followed by a written report in ten working days, after the investigator first learns of the event. A serious or unexpected complication would include those complications not generally expected in a heart valve patient.

Adverse events are defined by the United States FDA as complications, meaning:

"Operative mortality, morbid events, and consequences of morbid events. Complications may or may not be device related."

According to the European EN 540, an adverse event is defined as:

"Any undesirable clinical occurrence in a subject whether it is considered to be device related or not."

This study uses the term "complication" to mean any adverse event or adverse device effect (a device-related adverse event), which may be mild, moderate, or severe. If as a result of a complication during a clinical investigation a subject has to be hospitalized, if hospitalization is unduly prolonged because of potential disability, if hospitalization is unduly prolonged because of potential danger to life, if a reoperative intervention has been necessary, or if the event is terminal, the complication is regarded as severe.

The definitions which appear in the following sections will be used to report complications associated with the use of the On-X prosthesis. Complications will be recorded and dated when they are observed or estimated to have occurred and treatment(s) documented. An event will be recorded once unless there are multiple occurrences of that event. For example, a cerebrovascular accident (CVA) reported once with sequelae still present at subsequent follow-visits will not be reported again. If another CVA occurs that is unrelated to the initial episode, then it is reported as a separate incident.

When determining whether a complication is valve related this study will use the definitions of the AATS/STS guidelines. More specific guidance on these determinations is contained in the following discussions of the various types of complications. In any case, adequate documentation must be supplied to support the contention that a complication generally regarded as valve-related is not valve related. Information that pertains to reoperation, explant, and death must be recorded on the appropriate sections of CRF5 and/or 6. For death, the cause of death must be established, and an autopsy performed when possible. An explant analysis must be conducted in all cases when a valve is explanted whether by reoperation or autopsy. Attach supporting hospital reports when appropriate. Following completion of the information, the investigator must review, date, and sign the CRF.

Specific Instructions for Completing CRF5.

The complication form (CRF5) allows the identification of event type, and how each event was diagnosed and treated; what the outcome of the complication was; and what the patient's status at the time of the event was. Death from unrelated causes is also reported on CRF5. Details of any reoperation are given on a separate form (CRF6), which also asks for a description of any explant (from reoperation or autopsy). A separate CRF5 should be completed for each independent complication.

Study valve related reoperation is defined as any operation that repairs, alters or replaces a previously implanted study prosthesis, also included are operations that treat other valve related complications but do not involve surgery on this valve, i.e., surgery to resolve a hemorrhagic complication. This category also includes incidental replacement of the prosthesis, e.g., the patient undergoes surgery for a different cardiovascular procedure and the surgeon decides to remove the study valve. Cardiovascular surgical procedures other than repair or replacement of the study valve will also be recorded on the CRF5.

Death will be recorded as cardiac or not, and valve related or not. Valve related deaths include deaths from the following causes:

- thrombosis or thromboembolism;
- endocarditis;
- prosthetic valve dysfunction;
- anticoagulant related hemorrhage;
- hemolysis; and
- congestive heart failure, where documentation of a cause other than the valve cannot be given; and sudden unexplained death without autopsy which can definitely assign other causes than the valve.

Deaths caused by heart failure in patients with advanced myocardial disease and satisfactorily functioning prosthetic valves are not considered valve related. Any death that occurs within 30 days of reoperation for a valve related complication is considered valve related.

Classification of each complication is described in the sections that follow.

#### Thromboembolism

Thromboembolism is defined as any valve thromboembolus exclusive of infection. This includes any new focal or global neurological deficit (transient or permanent), myocardial infarction, prosthetic thrombosis, or peripheral arterial embolus.

A thromboembolic cerebrovascular accident (CVA) is an infarction of the central nervous system determined or suspected to be due to thromboembolism as diagnosed by imaging study with or without clinical symptoms.

A transient neurological event is defined as an abrupt onset of a focal neurological dysfunction caused by brain, spinal cord or retinal ischemia without acute infarction lasting at least one minute and no longer than 72 hours.

Intraoperative myocardial infarctions are not counted. Postoperative myocardial infarction is also not counted unless the infarction is caused by coronary embolus detected by operation, autopsy or clinical imaging. Emboli caused by non-thrombotic material (atherosclerosis, myxoma) are not counted.

Thrombi that are secondary to another primary complication; i.e., endocarditis, are recorded but also noted to be a secondary event by stating so in their etiology.

Excluded from the thromboembolism category are:

- Events which occur intraoperatively or within 24 hours of surgery due to myocardial infarction or stroke.
- Any peripheral arterial emboli proven to have originated from another cause, e.g., atrial myxoma.
- Failure to awaken from the surgical procedure.
- Pulmonary emboli.
- Events due to proven ischemic disease of the extremities.

However, if any of these complications occur, document the events anyway in the Complications Form.

For any thromboembolic event it is important to determine the INR of the patient at the time of the event, if possible. Every attempt should be made to do so.

#### Thrombosis

Thrombosis is any premortem thrombus adhering to or near the study valve that occludes part of the blood flow path or that affects valve function. This is listed as its own category and should be confirmed by reoperation (explant) or autopsy. Thrombolytic therapy, other than that used to stabilize a patient prior to surgery, is not recommended as a treatment for thrombosed valves. In this study suspected thrombosed valves are to be replaced through reoperation, wherever possible. Clinical judgment can be used to diagnose the presence of thrombosis (lack of normal prosthetic valve sound, prolonged lowered blood pressure, loss of consciousness, cardiovascular shock) if the clinical diagnosis is accompanied by a confirming medical test (echocardiography, cineradiography or angiography).

#### Bleeding Event

Bleeding Event is defined as any episode of internal or external bleeding in patients. Episodes immediately related to this surgery will be recorded as perioperative. This also includes any episode of hemorrhagic tamponade. The INR at the time of hemorrhage should be determined, if possible. These events will be classified as major or minor, and are defined as follows.

- Major: An episode of internal or external bleeding that causes death, permanent injury, operation, hospitalization, or requires transfusion or pericardiocentesis. Examples include nosebleeds that require outpatient transfusion, cerebral bleeding that results in neurological damage and/or death, and gastrointestinal bleeding that requires hospitalization.
- Minor: All other episodes of internal or external loss of blood. Examples include nosebleeds that do not require transfusion, hematomas due to trauma or surgery that do not require transfusion, and ocular hemorrhage. Bleeding or bruising from traumatic wounds are excluded, unless the bleeding goes uncontrolled enough to require intervention that would place the event in the major category.

#### Prosthetic Valve Endocarditis

Prosthetic valve endocarditis is defined as documented evidence of infection of the prosthesis based on histopathological evidence in a surgical or autopsy specimen and/or customary clinical criteria, including an appropriate combination of clinical signs (fever, new/altered cardiac murmurs, splenomegaly, systemic emboli, immunopathological lesions) and possibly positive blood cultures as available. The organism(s) involved should be identified whenever possible.

#### Prosthetic Valve Dysfunction

Prosthetic valve dysfunction is defined as any change in valve performance which results from intrinsic or extrinsic abnormalities that cause stenosis or regurgitation. Prosthetic valve dysfunction can be classified as structural deterioration, nonstructural dysfunction, or paravalvular leak.

#### a. Structural Valve Deterioration

Structural valve deterioration is any change in function of the prosthesis which results from an intrinsic abnormality that causes stenosis or regurgitation. The diagnosis can be based on an examination of the explanted or damaged valve or clinical investigation. Examples include excessive wear, leaflet escape, leaflet fracture, housing crack, leaflet pitting, or sewing ring deterioration. Excluded from this category is structural deterioration which results from endocarditis, paravalvular leak, and thrombosis.

#### b. Nonstructural Valve Dysfunction

Nonstructural dysfunction of the valve is any change in function of the prosthesis that results in stenosis or regurgitation which is not intrinsic to the valve. Examples

include patient-prosthesis mismatch, inappropriate positioning or sizing, leaflet entrapment by suture or pannus, paravalvular leak and hemolysis. The diagnosis should be based on examination of the damaged or explanted valve, or clinical investigation. Events to be excluded are those associated with endocarditis and thrombosis.

#### c. Paravalvular Leak

Any evidence of leakage of blood around the prosthesis between the sewing ring and native annulus. Diagnosis of paravalvular leak may be obtained from echocardiography; however, definitive diagnosis will be obtained at reoperation, explant, or autopsy. Indicate severity of the leak.

Indicate if the event is secondary to another valve-related complication, e.g., endocarditis, hemolysis, thromboembolism, thrombosis. Such events will be classified as major (required surgical or percutaneous intervention) or minor (does not require surgical or percutaneous intervention).

#### Hemolytic Anemia

Hemolytic anemia will be recorded as a complication in all cases of hemolytic anemia that are attributable to the valve, based on usual clinical criteria, such as easy fatigability, dyspnea, faintness, pallor, rapid pulse, low blood pressure or other common signs of anemia, and which require intervention: such as long-term iron supplement, transfusion, prosthesis replacement, etc. Indicate if hemolytic anemia is primary or secondary to another valve related adverse event (e.g., paravalvular leak). Events that are not considered valve-related are those due to liver disease, myocardial infarction, or systemic infection, where these causes are confirmed by other clinical evidence.

Hemolytic anemia that requires intervention will be considered to be clinically significant hemolytic anemia. Hemolytic anemia that does not require intervention will be considered to be clinically insignificant hemolytic anemia and will be reported. Hemolytic anemia should be distinguished from compensated hemolysis or compensated hemolytic state, where the hematocrit is stable and there is no anemia because increased red blood cell production is able to keep up with accelerated red blood cell destruction from hemolysis.

For purposes of this clinical trial, hemolysis is defined from blood studies alone by the following inclusive criteria, but is not reported as a complication until associated with anemia that is treated medically or surgically (i.e. clinically significant hemolytic anemia). Thus, hemolysis and clinically significant hemolytic anemia are analyzed separately.

#### Ongoing hemolysis:

- Serum lactate dehydrogenase greater than 200% of the upper normal limit;
- Reticulocyte count of at least 4.0%;

- Plasma free hemoglobin above upper limit of laboratory normal;
- Reduction of 20% in haptoglobin below normal range; and
- Untreated clinical sequelae (once treated this becomes hemolytic anemia).

Hemolytic anemia by laboratory test additionally requires:

- Hematocrit below laboratory normal range;
- Hemoglobin below the laboratory normal range;

#### **Unanticipated Valve-Related Event**

It is unknown what kind of event would qualify, but in case any unknown valverelated complication should arise that does not meet any other defined criterion, pleased record on the Complications Form. Should this happen this event must be reported to the monitor immediately, since it is likely to create immediate regulatory reporting requirements. An occurrence of an unknown negative effect is very serious and must not be left unreported for any length of time.

#### Congestive Heart Failure

Congestive heart failure will be considered valve related if the event is new and is not continued from a preoperative heart failure condition, and is caused by one of the following prosthesis-related events: Anticoagulant-related hemorrhage, endocarditis, hemolysis, nonstructural dysfunction, paravalvular leak, structural deterioration, thromboembolism, thrombosis, or reoperation.

The most common causes of non-valve related congestive heart failure are coronary artery disease, hypertension, valvular heart disease (due to a valve other than the study valve), cardiomyopathy, cor pulmonale, congenital heart disease, or unknown causes. When an event is considered not valve related the reasons for that decision must be recorded.

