Valve Orientation: Check the most accurate valve orientation description below based upon the direction of the valve axis.  Aortic: □LC/RC Commissure □RC/NC Commissure □NC/LC Commissure □Other, describe:  Mitral: □Anatomical □Anti-anatomical □Other, describe:					

Investigator Signature: \_\_\_\_\_ Date (m/d/y): \_\_\_\_/\_\_\_\_

Institution: Investigator:	ON-X LIFE TECHNOLOGIES On-X® 17mm Aortic/23mm Mitral Stud CRF 4 Follow Up		Patient Initials 2010-01, Rev H	
Visit Date (m/d/y)/		☐ PostOperative/Discha	rge	
		Early (3 to 6 months)		
		☐ 1-Year (11 to 14 mon	ths)	
		Off Schedule		
(If follow up	ost to Follow Up: Efforts to Contact and		RF 5)	
Type of Examination: Office	Outpatient Hospit	al Telephone Doth	er	
NYHA Class:		□ IV □ Unkn	own	
Cardiac Rhythm:	Sinus Paced Atrial Fibrillation	Regular Irregular Other, specify:		
Anticoagulant	None	☐ Warfarin/Coumadin		
Therapy:	] Clopidogrel	☐ Heparin		
	Aspirin	Other		
INR Blood Collection Date (m/d/y):/ (closest to date of visit)				
New Complications: (Since last follow up) Yes No (Complete complication form, CRF 5)				
Echo Completed (m/d/y) Attach CRF 2 and send echo, applicable at discharge, 3-6 months and 1 yr follow-up.				
Investigator Signature: Date (m/d/y):/				

	ution: itigator:	ON-X LIFE TECHNOLOGIES On-X® 17mm Aortic/23mm Mitral Study CRF 5 Complications 1 of 2	Patient Initials 2010-01, Rev H	
	Date (m/d/y):/			
Etiolo	ogy:			
Compl	lication Type (complete 1 for	m for each event) Complicatio	n number:	
_	_	eurologic: TIA Peripheral: Major		
		□ CVA □ Minor		
		☐ Fatal		
2 [	☐ Valve Thrombosis			
3.	☐ Bleeding Event ☐ Major ☐ Minor ☐ Cerebral ☐ Cardiac ☐ Ocular ☐ GI ☐ Nosebleed ☐ Hematoma ☐ Other ☐ Anticoagulant related ☐ Antiplatelet related ☐ Not drug related			
4.	Prosthetic Endocarditis (O	rganism:)		
	Risk Factor: Denta	l Work ☐ IV Drug Use ☐ Recent Inf	ection Other	
5. 	Prosthetic Valve Dysfunct	ion		
	☐ Nonstructural ☐ Structural ☐ Paravalvular Leak	(Type:	)	
6. E	Hemolytic Anemia (condu	ct blood tests)		
7.	Congestive Heart Failure	☐ Valve Related ☐ Not V	Valve Related	
8. C	Reoperation	☐ Repair ☐ Explant		
9.	Other Valve Related	Explain:		
10.	Death - Primary Cause:	☐ Valve related ☐ Other cardiac ☐ Other cardiac (continues next page)	ther Unknown	

Institution: Investigator:	On-X ® 17mi	LIFE TECHN m Aortic/23m CRF 5 omplications 2	m Mitral Study	Patient Initials 2010-01, Rev H
Complication number:				

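### The complication rule and the death rule set opposite defaults for heart failure of undocumented cause, and CRF5 does not link them

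*Combined protocol and SAP*

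**What the plan says.** Section 2.4.5 has two rules that bear on heart failure.

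- **Complication rule (Congestive Heart Failure).** The event is valve related if it is new, does not continue a preoperative condition, and "is caused by one of the following prosthesis-related events", after which the causes are listed. The next paragraph gives the usual causes of non-valve-related heart failure and ends "cardiomyopathy, cor pulmonale, congenital heart disease, or unknown causes". It closes with a documentation duty: "When an event is considered not valve related the reasons for that decision must be recorded".
- **Death rule (list of valve-related deaths).** Deaths counted as valve related include "congestive heart failure, where documentation of a cause other than the valve cannot be given". The same entry goes on to cover deaths that remain unexplained: "sudden unexplained death without autopsy which can definitely assign other causes than the valve". There is one exception: "Deaths caused by heart failure in patients with advanced myocardial disease and satisfactorily functioning prosthetic valves are not considered valve related".

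The text provides for each death to be classed as cardiac or not and as valve related or not. It also requires the cause of death to be established.

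In Appendix B, CRF5 item 7 asks whether heart failure is valve related or not. Item 10, headed "Death - Primary Cause", offers valve related, other cardiac, other and unknown. Page 2 of CRF5 has a separate yes/no box for valve relatedness.

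Section 2.0 (Valve safety) commits the study to incidence and rates for all deaths and for each valve-related cardiovascular complication. Sections 2.0 and 2.4.10 compare these with the original PMA results.

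**The concern.** When the cause of heart failure is not known, an analyst needs one stated default. Here there are two, and they point in opposite directions. Which one applies depends on whether the patient died, and nothing in the plan says that this difference is intended.

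Two things are at stake. First, a fatal episode can carry conflicting codes on the study's own form. Second, a new, non-fatal episode with no established cause is left out of the valve-related complication rate. That default favours the device, in a study where a single event visibly moves any rate.

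**Working it through.** The documents give no planned count or rate of valve-related heart failure, so there is no figure to reproduce. The check compares the rules and then shows the size of one reclassified event.

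**Step 1. Apply each rule to the same facts:** new postoperative heart failure, cause not documented.

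| | Complication rule | Death rule |
|---|---|---|
| Test for valve related | New, and caused by a listed prosthesis event | No other cause can be documented |
| Undocumented cause | Named among the non-valve causes | Meets the test |
| Result | Not valve related | Valve related |

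The exception in the death rule does not remove the difference. It needs advanced myocardial disease and a valve that works well, which is a known explanation rather than a missing one.

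**Step 2. Follow a fatal episode onto CRF5.** Under the complication rule, item 7 is marked not valve related. Under the death rule, item 10 should be valve related. Item 10 also allows unknown, and no instruction says how that choice maps to the yes/no box on page 2. An investigator could pair unknown with no, even for a death that the text counts as valve related.

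**Step 3. Follow a non-fatal episode.** Only the complication rule applies, so the event is left out of the valve-related count. The duty to record reasons does not prevent this, because an unknown cause is itself on the list of accepted reasons.

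**Step 4. Size of one event.** Section 1.0 gives at least 15 and approximately 20 patients, followed for 1 year. Proportion = x / n, with exact (Clopper-Pearson) 95% intervals:

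- n = 15: 0/15 = 0% (0 to 21.8%); 1/15 = 6.7% (0.2 to 31.9%).
- n = 20: 0/20 = 0% (0 to 16.8%); 1/20 = 5.0% (0.1 to 24.9%).

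As a linearized rate, assuming each patient contributes one full year, with exact Poisson 95% intervals:

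- 1 event in 15 patient-years = 6.7 per 100 patient-years (0.2 to 37.1).
- 1 event in 20 patient-years = 5.0 per 100 patient-years (0.1 to 27.9).

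These figures hold for any single event in a study of this size. They are not a forecast of how often unexplained heart failure will occur.

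**The case against.** The strongest reply is that the two rules govern different records. One classifies a complication, the other a death, and a stricter default for deaths is a coherent choice. The list of non-valve causes can also be read as descriptive, and the criterion sentence says if rather than only if.

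Part of this stands. The death rule decides the fatal case, so a reader who inferred that the valve-related death count cannot be determined would be going too far. The rest does not dispose of the point. An undocumented cause cannot be shown to meet the complication criterion, the only place the definition names it is among the non-valve causes, and the plan nowhere says that the asymmetry is deliberate.

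Other stronger readings are also unsupported:

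- **That the general burden of proof already settles heart failure.** The text says "adequate documentation must be supplied to support the contention that a complication generally regarded as valve-related is not valve related". That covers complications generally regarded as valve related. The status of heart failure is made to depend on its cause, so the sentence does not clearly reach it.
- **That obstruction from a small valve would be missed.** Patient-prosthesis mismatch and inappropriate sizing are given as examples of nonstructural dysfunction, which is a listed valve-related cause of heart failure. Echocardiography is required at discharge, 3-6 months and 1 year. Recognised obstruction is therefore covered, and the gap concerns only cases whose cause is not established.
- **That the unknown option on CRF5 leaves valve relatedness unrecorded.** The page 2 box can record it. What is missing is a rule joining the two items.
- **That every death of unknown cause should count as valve related.** The death rule reaches only heart failure without a documented other cause and sudden unexplained death without a definitive autopsy.

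It is also fair to say that the plan itself warns that its rates are of limited value, and that the wording used for the PMA data is not visible here. If the PMA used the same definition, changing it on one side only would harm the comparison.

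**Conclusion.** The point holds in a limited form. For heart failure of undocumented cause, the complication rule defaults to not valve related and the death rule to valve related. A fatal episode can therefore carry opposite codes at CRF5 items 7 and 10, and non-fatal unexplained new heart failure leaves the valve-related complication rate in the device's favour.

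The reach is modest. The valve-related death count follows from the death rule. All-cause mortality does not change. Heart failure is not among the primary safety endpoints named in section 2.0, so the exposure lies in the wider commitment to report each valve-related cardiovascular complication and compare it with the PMA data. One reclassified event moves the proportion by 5.0 percentage points with 20 patients or 6.7 with 15. The conclusion rests on the wording alone; it assumes nothing about how often such events occur or about how the PMA or the cited reporting guideline treats them.

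**What to change.** 1. **Congestive Heart Failure definition.** Remove unknown causes from the non-valve list, and state that new postoperative heart failure with no documented non-valve cause is counted as valve related, consistent with the death rule. The deletion alone is not enough, because the criterion sentence still asks for a listed prosthesis event.
2. **Comparison with PMA data.** If the control data were classified under the present wording, also report the rate under that wording, so that like is compared with like.
3. **CRF5.** Keep unknown as a cause of death, so that investigators need not guess. State that a death from heart failure with no documented other cause, or a sudden unexplained death without a definitive autopsy, must be marked yes in the page 2 valve-related box. State also that this box determines the valve-related death count.

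The cost is a few sentences in section 2.4.5 and one form instruction. The valve-related rate may come out slightly less favourable. The change affects event classification only, not patient care.
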